F4. Review to detect presence or absence of hypoxemia indicative of ARDS: In order to further eliminate the unnecessary detailed record review, a focused review of the transfusion episode will be performed to detect hypoxemia occurring within six hours of completion of transfusion. Medical records will be reviewed for the respiratory status within six hours after the completion of the study unit transfusion to detect the following: Oxygen saturation (SpO2) less than 90% by pulse oxymetry without or with oxygen therapy; ratio of SpO2/FiO2 <315; and ratio of PaO2/FiO2 <300 on arterial blood gas analysis. FiO2 will be calculated for patients receiving oxygen by cannula or mask as follows: 1 liter = 0.21; 2 liters = 0.23; 3 liters = 0.25; 4 liters = 0.35; 6 and 7 liters = 0.45, and 8, 9, and 10 liters = 0.49 (Rice TW 2007).

If hypoxemia is documented, a detailed medical record review will be performed by the record review coordinator. The full extended data form will be completed. A Power Point summary of the major events and timeline will be prepared. The completed extended data forms and summaries will be sent to the Triage MD for further review.

Precise incidence rates for hypoxemia as defined in this manner in hospitalized patients are not available. Most of the data on incidence of acute respiratory failure (ARF) are reported in patients who are treated in the intensive care unit (ICU). For example, Flaatten et al have reported an incidence of ARF of 63% among 832 patients treated in the ICU. In 13,346 ICU admissions, 1,231 (9.2%) patients were found to have acute respiratory failure by Luhr et al. Pettila et al have described an incidence of ARF of 32.5% in 520 ICU patients while Vincent et al found that 32% of the 458 ICU patients had ARF at admission to the ICU and 35% of the 991 ICU patients developed ARF during their stay in ICU. Roupie et al report that 43% of the ICU patients required mechanical ventilation. A combined rate of 16% for ARDS and ALI in 1977 ICU admissions has been observed by Bersten et al. These data show a wide range for ARF in ICU patients. In order to be more conservative in our estimates for the number of charts requiring detailed review, we have estimated that 60% of the study patients would have hypoxemia/acute respiratory failure and would therefore require detailed chart review along with a review by a triage critical care physician (see below).

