component and notify the record review coordinator of which components were issued for transfusion to whom (See Appendix B for a draft letter).

F12D. Record review coordinator's approach to radiology reports and hypoxemia data collection: The record review coordinator(s), who would either be a staff at the hospital, hired by each blood center or one approved at the hospital, will perform a search of radiology records. This search can involve either electronic records or paper records. The coordinator will collect the reports as described above for the local PI's determination as to the need for further record review. The coordinator will perform the medical record review of those records that are pertinent (24 hours before and 24 hours after the transfusion of the study unit) to detect hypoxemia.

F12E. Training of record review coordinator: Depending upon the requirements of the hospitals where the record review is to be conducted, the record review coordinator(s) may undergo training similar to the one that honest brokers have to undergo to become certified. The certification protocol to become an honest broker is available from the University of Pittsburgh Medical Center and is attached as Appendix C. Also, depending upon the hospital's specific requirements, a possible alternative to hiring the staff/s at the hospital or at the blood center as record review coordinator/s may include a contracted service to conduct the record review. Additional training specific to the manner by which medical record reviews are to be done will be provided to each coordinator (see below).

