G.1. Limitations of retrospective medical record review: One of the limitations of a retrospective medical record review study is that some clinical findings may not be recorded in a patient's chart. However, it is highly unlikely that major clinical findings such as severe respiratory distress would not be recorded. Conversely, milder signs and symptoms may not be recorded and it is therefore possible that milder cases of TRALI (e.g., those in which hypoxemia is not severe) as well as milder cases of pulmonary dysfunction that fall short of the diagnosis of TRALI may be missed. However, TRALI experts are unsure if mild forms of TRALI exist. Since certain clinical data are almost always recorded including arterial blood gas analysis results, chest x-ray interpretations, electrocardiogram results, brain natriuretic peptide (BNP) measurements, echocardiogram interpretation, white blood cell counts, and vital signs including temperature, the retrospective study design proposed in this research should allow for comprehensive detection of clinically-significant forms of TRALI.

A large number of blood recipients must be studied to confidently identify a difference in TRALI risk from an antibody positive vs. antibody negative component. To accomplish this practically, a stepwise method for recipient record review is proposed. First, a patient must have had a chest x ray within 24 hours of the time the blood was issued. Second, the radiology report must indicate the presence of new or worsening bilateral lung infiltrates/pulmonary edema for the patient's record to be reviewed further. Third, hypoxemia must be documented. Fourth, a critical care specialist will review the cases at this point primarily to exclude or triage cases of TACO

prior to forwarding the case to the medical board for review. Since a retrospective data collection study is by design inefficient compared to a prospective study, this stepwise approach described reduces the labor needed for medical record review and yet allows follow up of a large number of recipients.

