- the proportion of TRALI due to HLA antibodies (i.e. immune-mediated)

Additional analyses will involve estimating TRALI incidences and other incidences. Analysis will be conducted to assess the incidence of TRALI and possible TRALI per unit transfused and per transfusion recipient. For this analysis the number of units transfused per episode per patient will be derived from the data available in the data collection forms. Incidence will also be calculated, when possible, for (a) TRALI without other risk factors and TRALI with other risk factors, (b) among those with other risk factors, incidence will be calculated for ALI which cannot be distinguished from TRALI and for ALI that is not TRALI but that occurred within 6 hours or >6 hours of transfusion.

Analysis of other incidences is described below. In addition to the transfusion complications described above, incidence for transfusion-associated cardiac overload will be based on cases that are classified by the Medical panel as TACO.

Using appropriate statistical methods, associations will be explored between different transfusion complications described above (TRALI, no-TRALI, possible TRALI, ALI of undetermined origin, TACO) and the underlying clinical information, such as, demographics, diagnosis (CPT codes), co-morbid conditions (e.g. renal failure), degree and severity of hypoxemia, chest x-ray and cardiac abnormalities. Data, when available, will be correlated with the presence of HLA and HNA antibodies (signal strength and/or specificity of antibodies) in the recipients as well as the involved donors and their HLA and HNA phenotypes to assess the antibody specificity and the corresponding cognate antigens in donor/recipient pairs among different groups of patients with complications described above. Frequencies of clinical symptoms of transfusion complications will be ascertained. Recipient outcome data, when available, will be tabulated for different types of transfusion complications. Clinical characteristics of the cases that were reported to the blood bank before the study and after the study will be compared.

M. Timeline

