- **2.** Record the date and time which is nearest to the time of study unit transfusion if there is more than one chest X-ray taken within 24 hrs prior and 24 hrs after the study unit transfusion

Appendix G: Extended Data Collection Form LEUKOCYTE ANTIBODIES PREVALENCE STUDY – PHASE II EXTENDED DATA COLLECTION FORM

Please refer to clinical information from daily chart notes, laboratory test results, radiology reports, echocardiogram reports, discharge summary, nursing notes, blood bank issue and transfusion forms and other chart records to complete this form.

SECTION A: GENERAL INFORMATION

DATE:		ABSTRACTED BY	:						
SOURCE O	SOURCE OF INFORMATION: (Check all that apply)								
ELECTRONIC RADIOLOGY REPORTS DATABASE									
ELECTRON	ELECTRONIC MEDICAL RECORDS INCLUDING RADIOLOGY REPORTS								
PAPER MEDICAL RECORDS									
OTHER (SPECIFY)									
BUI #	BUI #								
		ED EVIDENCE THAT INDEX BLOOD RANSFUSED?	YES Stop data collection	NO Continue					

SECTION B: ADMISSION & DISCHARGE

			DATE	Т	IME (Military)		
HOSPITAL	ADMISSION DISCHARGE						
HUSPITAL				(when available)		
ICU	ADMISSIC	ON					
100	DISCHARGE						
DISCHARGE ST	FATUS	ALI	VE DECEASED				
DISCHARGE D codes. Collect onl	IAGNOSIS L y if NOT prev	.ist up viously	to 10 diagnosis and assigneed in Screening For	0 10 diagnosis and assign ICDDESCRIPTIentered in Screening FormDIAGNOSIS			
				1.			
				2.			
			3.				
				4.			
				5.			
				6.			
				7.			
				8.			
				9.			
				10.			

SECTION C: PATIENT DEMOGRAPHICS

AGE					GENDER	MALE	FEMALE
WEIGHT	HT UNIT			HEIGHT	UNIT		
RACE/ETH	w	B	H	A	Other		

SECTION D: TRANSFUSION ADMINISTRATION

DATE OF Tx:			тім	TIME OF Tx:				AM		РМ	
	List BUI numbers of all involved products and their ABO/Rh type (within 6 hours prior to the onset of reaction):										
BUI #	UI # ABO/Rh			#	ABO/	BO/Rh BUI #		ABO/RI)/Rh	
								-			
VITAL SIGNS (See Note 1) BP (mm		BP (mm	Hg) PULSE/MIN		/MIN	R	RESP/MIN		TEMP (degree F)		
BEFORE Tx:											
1/2 HR DURIN	G:										
1 HR DURING	6 :										
2 HR DURING	; :										
AT COMPLETI OF Tx:	ON										
TX REACTION: (Within 6 hrs of completion of unit)		pletion of	YES			-	REPORTED TO BLOOD BANK:		YES 🗌 NO 🗌]
TYPE OF REACTION: (Describe) See Note 2											

SECTION E: HYPOXEMIA EXCLUSION CRITERIA

Concentrate the chart review process around the time window of 24 hours prior and 24 hours after transfusion of study unit. Please complete respiratory status within **six hours** of completion of the transfusion.

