
Estimate FiO2 as follows, if patient is receiving oxygen by nasal cannula or mask.

Room air: 0.21	1 Liter of O2: 0.23	2 Liters of O2: 0.25	3 Liters of O2: 0.27
4 Liters of O2: 0.30	5 Liters of O2: 0.35	6, 7 Liters of O2: 0.40	8, 9, 10 Liters of O2: 0.49

If receiving oxygen therapy with mechanical ventilation, use percent oxygen recorded on the patient's respiratory care data. Review ventilator data to find FiO2 value (eg. 405 oxygen administration equals a FiO2 of 0.4).

RESPIRATORY STATUS	YES	NO	NR
Oxygen saturation (SpO2) less than 90% by pulse oxymetry without oxygen therapy?			
Oxygen saturation (SpO2) less than 90% by pulse oxymetry while receiving oxygen therapy			
Ratio of SpO2/FiO2 <315 (See Note 1)			
Ratio of PaO2/FiO2 <300 (PaO2 = oxygen saturation on arterial blood gas analysis) (See Note 2)			

If answer to **ANY** of the above respiratory status items is **YES** then further chart review is required. If answer to **ALL** of the above respiratory status items is **NO** then stop now and send copy of form to Westat.

NO.	ITEM	YES	NO	NR	START DATE (If applicable)	RESOLVE DATE (If applicable)	NOTES
1	Acute CNS Injury (within 7 days before Tx)				applicable)	applicable)	Note 3
2	Acute renal failure (within 7 days before Tx)						Note 4
3	Aspiration						Note 5
4	Bone marrow stem cell transplant in past 12 months						
5	Burn as an admitting diagnosis (if within 48 hrs before reaction)						
6	Cancer or recent (within 1 month) chemotherapy						
7	Cardiac bypass during current admission (within 48 hrs before reaction)						
8	Cardiac ischemia during current admission (within 7 days before Tx)						
9	Hx of chronic alcohol abuse						Note 6
10	Hx of chronic renal failure						Note 7
11	Congestive heart failure during current admission (within 7 days before Tx)						Note 8
12	Hx of coronary artery disease						
13	Hx of diabetes mellitus						Note 9
14	DIC during current admission (within 7 days before Tx)						Note 10
15	Drug overdose as admitting diagnosis (within 48 hrs before reaction)						
16	Exposure to high altitude as admitting diagnosis (within 48 hrs before reaction)						
17	Heat stroke as admitting diagnosis (within 48 hrs before reaction)						
18	Hemorrhagic shock during current admission (within 48 hrs before reaction)						
19	High INR (>3.0) during current admission (within 7 days before Tx)						
20	Hx of immunosuppression						
21	Just underwent surgery (within 48 hours)						

SECTION F: PATIENT HISTORY & CLINICAL FINDINGS

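### The planned incidence of non-TRALI ALI more than 6 hours after transfusion is biased downward, because charts go to review only if a hypoxemia criterion is met within 6 hours

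*Protocol*

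**What the plan says.** **The planned estimate.** Section L lists additional incidences after the primary comparison. The list opens with a hedge: "Incidence will also be calculated, when possible, for (a) TRALI without other risk factors and TRALI with other risk factors". Part (b) is restricted to recipients with other ALI risk factors and includes an incidence "for ALI that is not TRALI but that occurred within 6 hours or >6 hours of transfusion". The diagnosis of ALI is assigned by the expert panel (F21).

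**The route to the panel.** After the chest x-ray step, F4 says that "a focused review of the transfusion episode will be performed to detect hypoxemia occurring within six hours of completion of transfusion". What follows depends on the result: "If hypoxemia is documented, a detailed medical record review will be performed by the record review coordinator", and the extended form and summary then go to the triage physician. G1 lists the same step in the sequence: "Third, hypoxemia must be documented".

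**The form.** Appendix G Section E asks for respiratory status in the six hours after the transfusion is completed. Any YES among its four items leads to further review. If all four are NO, the coordinator is to "then stop now and send copy of form to Westat".

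**The other window.** F12D describes the coordinator's review as covering records "24 hours before and 24 hours after the transfusion of the study unit) to detect hypoxemia". Section E also opens with a 24-hour span: "Concentrate the chart review process around the time window of 24 hours prior and 24 hours after transfusion of study unit". Its next sentence narrows the respiratory items to six hours.

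**The concern.** The hypoxemia screen was built for TRALI, and six hours suits TRALI because F25 ties its blood-gas criterion to that interval. Section L uses the same screened charts for a different quantity, ALI arising after six hours. Consider a recipient with new bilateral infiltrates on the 24-hour film, adequate recorded oxygenation up to hour 6, and first hypoxemia at hour 10. This is a natural member of the late category, yet the chart closes at Section E and is never classified.

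A late incidence could still be computed from the charts that do pass. If it were printed beside the early incidence with all recipients as denominator, the two figures would rest on different ascertainment and the late one would be too low. The hedge in Section L does not tell the reader this. The mismatch between F12D and F4 adds a practical risk: coordinators at five centers could apply the screen differently.

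**Working it through.** This is mainly a check of whether the planned quantity can be observed. The arithmetic only gives the scale.

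**1. The plan's own chart numbers (F3 to F5, Table-4).**
- Recipients reviewed: 2,590
- Post-transfusion chest x-ray, 40%: 2,590 × 0.40 = 1,036
- New or worsening bilateral infiltrates, 50%: 1,036 × 0.50 = 518
- Hypoxemia, 60%: 518 × 0.60 = 310.8, stated as 311

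The stated 311 reproduces. Charts stopped at the hypoxemia step: 518 − 311 = 207, and 207 / 518 = 40%.

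**2. The same proportion in the pilot (F6).** Recipients with pulmonary edema on x-ray: 3 community + 12 tertiary = 15. With hypoxemia within six hours: 2 + 6 = 8. Without: 15 − 8 = 7, and 7 / 15 = 47%.

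Both figures count charts closed without an ALI classification. Neither counts late ALI cases.

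**3. Who can enter the late category.**

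| Course of the recipient | Section E result | Reaches triage and possibly the panel? |
|---|---|---|
| First hypoxemia after hour 6, all four items recorded NO | stop | No |
| Any criterion met by hour 6, ALI developing later | continue | Yes |
| Mixture of NO and not recorded (NR) | no rule on the form; F4 and G1 require documented hypoxemia | Unclear |

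The second row is not empty. Section E does not ask for the hypoxemia to be new, so earlier hypoxemia or hypoxemia from another cause passes. A chart can also pass on SpO2 below 90% alone. With SpO2 of 89% and the FiO2 values in Section E:
- Room air: 89 / 0.21 = 424
- 3 liters: 89 / 0.27 = 330

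Both ratios are above 315. Note 21 of Appendix G dates a reaction by a blood-gas ratio below 300, a saturation ratio below 315, or edema on x-ray. Such a chart can therefore pass early and still have its onset dated after hour 6.

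For charts that pass, the later parts of Appendix G hold the necessary data: highest FiO2 in the following 24 hours, an ARDS diagnosis within 24 hours, and blood gases to 35 hours 59 minutes. For charts stopped at Section E these parts are not completed, so the missed cases cannot be recovered from the study database.

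**4. Direction and possible size of the bias.** The documents give no late-ALI rate, so this is an illustration on an assumption: 10 true late cases among 2,590 recipients, or 10 / 2,590 = 3.9 per 1,000.

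| Share of late cases that also met a criterion within 6 h | Observed incidence |
|---|---|
| 0% | 0 per 1,000 |
| 25% | 10 × 0.25 / 2,590 = 1.0 per 1,000 |
| 50% | 10 × 0.50 / 2,590 = 1.9 per 1,000 |

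The observed value equals the true value multiplied by a share that the design cannot estimate.

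**5. The two windows.** If F12D's 24 hours is the detection rule, late hypoxemia would be found, but that contradicts F4 and the Section E instruction. If 24 hours is only the span of records consulted and six hours is the criterion, as the consecutive sentences in Section E suggest, then F12D is worded too broadly and the truncation stands. The text needs correction on either reading.

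**The case against.** A reader might go further and infer that late ALI cannot be observed at all, that its incidence will be near zero by construction, or that the 207 stopped charts contain every late case. The documents do not support this. The screen accepts any hypoxemia within six hours, new or not; the form follows charts that pass well beyond six hours; and the stop rule covers only charts with all items NO. Complete loss applies only to ALI whose first hypoxemia comes after hour 6.

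The 207 should not be read as a measure of the loss. The 60% behind it is a workload assumption, chosen on the high side because F4 had no precise hypoxemia rates. Nothing says how many of those recipients have ALI.

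A reader might also suppose that the protocol uses an early-versus-late ALI contrast as background for judging TRALI. No section plans that contrast.

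The defence can add that Section L hedges the estimate, limits it to recipients with other risk factors, and places it among additional analyses outside the primary and secondary objectives. That limits the importance of the point. It does not answer it: the hedge does not disclose that entry to the late category depends on meeting an early criterion, and a number could still be computed and reported as an incidence.

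Finally, F12D may be loose wording rather than a rival rule. That is plausible, but the coordinators need one window.

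**Conclusion.** The point holds in a limited form. If F4 and Appendix G Section E are followed as written, late ALI is ascertained only among recipients who also met a hypoxemia criterion within six hours of the end of transfusion. The incidence beyond six hours in Section L is then too low by an unknown factor, though not necessarily zero. On planning figures, 207 of 518 infiltrate-positive charts (40%) close at this step; the number of late ALI cases among them cannot be learned from this design. The conclusion assumes that the six-hour window governs; if F12D governed, the truncation would ease but the contradiction would remain.

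The primary TRALI comparison is unaffected. The matter concerns what may be claimed from one additional analysis, and the consistency of the hypoxemia window across three places.

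**What to change.** 1. In Section L, delete the incidence beyond six hours. Alternatively, keep it with a label stating that it is conditional on a hypoxemia criterion within six hours, and do not present it as an incidence among all recipients.
2. Reconcile F4, F12D and Appendix G Section E so that they give the same hypoxemia window. If 24 hours is the span of records to consult and six hours the criterion, F12D should say so.

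Both are text changes with no added data collection.

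A fuller alternative would record hypoxemia after hour 6 as well, with its time of onset, and send those charts for ALI classification. It is not cheap. At the budgeted 3 hours of detailed review plus 1 hour of slide preparation per chart, the upper bound is 207 × 4 = 828 coordinator hours across the five centers, before triage and panel time. G1 explains that the stepwise screen exists to limit such labor, so this is worth considering only if the late incidence is truly wanted.

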F5. Triage critical care physician review: Based on these considerations, the number of charts that would require a review by a triage critical care specialist will be 311 (60% of 518). The triage physician would receive the case summaries in the form of several PowerPoint slides per case along with the detailed medical chart data consisting of completed extended data form for each case and digital images of chest x-rays. The triage MD will be blinded as to the type of study component transfused. The review will be performed by a single MD and all REDS-II Centers will send records for review to the triage MD. The major aspect of this review is to determine if there is sufficient information to conclude that the patient has moderate to severe TACO. If such is the case, the triage MD will complete the form indicating the presence of TACO and no further reviews will be required. The number of cases that will be excluded from further review by the triage MD is uncertain, but may amount to 50%. If the percent is lower, then the workload for the Medical Review Board may need to be reassessed during the conduct of the study.

The above described processes are shown in the flow chart on next page and in Table-4 below.

Parameter	Number of patients	Comment
Number of patients needed for	1175	Based on 90% power calculations, for
each study arm		each arm of the study
Including ten percent margin	1,275	Margin added to account for missing
		records, deaths within six hours etc.
Total number of patients	2,590	Two equal groups of antibody positive
		and antibody negative component
		recipients
40% of patients with a post-	1,036	No. of post-transfusion chest x-rays
transfusion chest x-ray		needing a review
20% of patients with a pre-	518	No. of patients with a pre-transfusion
transfusion chest x-ray		chest x-ray
Total number of chest x-rays	1,554	No. of chest-rays needing a review

Table-4: The stepwise approach to record review with corresponding estimated activity numbers for the five REDS-II Centers

50% of post-transfusion chest x- rays showing new or worsening bilateral infiltrates/pulmonary edema	518	No. of patients requiring hypoxemia determination review
60% of the study patients would have hypoxemia	311	No. of patients with evidence of hypoxemia

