No. medical charts requiring detailed chart review including preparation of PowerPoint synopsis and then further Triage MD review	311	An unknown number of cases will be diagnosed as TACO and will have no evidence for ALI; these will not need to be forwarded to the Medical Review Board for adjudication. Total number of forwarded charts will be less than 311

F6. Pilot study to validate assumptions for proportions of patients with chest x-ray, pulmonary edema, and hypoxemia: A medical record review was conducted at Pittsburgh Center by research nursing staff on 66 randomly selected units of FFP transfused to 66 patients in Pittsburgh area hospitals. Twenty two patients were at a community hospital and 44 patients at a tertiary care hospital. Chest x-ray data was extracted from a radiology electronic database with radiologist's interpretation. A chest x-ray was considered present if done within 24 hours of the end of the index transfusion. Those reports indicating pulmonary edema, bilateral pulmonary congestion or bilateral infiltrates were then evaluated for hypoxemia. Hypoxemia was sought in the laboratory section of the patient's electronic medical record and was defined as: SO2/FiO2 of <315 or pO2/FiO2 of <300 within 6 hours of the end of the FFP transfusion.

At the community hospitals, 5 of the 22 (23%) had a chest x-ray within 24 hours of the transfusion; 3 of the 5 (60%) had pulmonary edema, and 2 of the 3 (66%) had hypoxemia. At the community hospitals, 2 of the 22 (9.1%) of the recipients would require an extended record review.

At the tertiary care hospitals, 24 of the 44 (55%) recipients had a chest x-ray within 24 hours of the transfusion. Twelve of the 24 (50%) had pulmonary edema and 6 of the 12 (50%) had hypoxemia. These data indicate that 6 of 44 FFP transfusion recipients at tertiary care hospitals would require extended record review.

It should be noted that of the six recipients at the tertiary care hospitals who had pulmonary edema on chest x-ray after the transfusion, four had pre-existing pulmonary edema on pre-transfusion chest x-ray.

The above pilot study supports our assumptions regarding the stepwise record review process.

F7. REDS-II Blood Centers to identify blood components from LAPS donors:

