A list of the components that were supplied to each participating hospital will then be printed by the blood center and provided to each corresponding transfusion service medical director or designated individual to identify corresponding recipients and to have the radiology and the medical records be abstracted by the record review coordinator(s). All information will be tracked and compiled into the tracking and data management systems either directly by research staff at the blood center/blood bank or by Westat, if forms are mailed to the coordinating center for data entry.

The coordinating center will be responsible for formation of the medical review board. The medical review board will assess all completed data forms in a blinded manner to determine the presence or absence of TRALI as described above. The coordinating center will compile the results of these reviews into the data management system to allow for formation of a database that will be used for analyses. The proposed diagnostic criteria for TRALI are detailed in the next section.

F25. Proposed Diagnostic criteria for TRALI: Using the Canadian Consensus Conference criteria, the medical review board will be responsible for reviewing the completed recipient forms and determining the presence or absence of TRALI (Kleinman et al).

- 1. New hypoxemia must be present and hypoxemia is defined as pO2/FiO2 ratio of <300 within 6 hours of completion of transfusion or venous oxygen saturation (SpO2) of less than 90% on room air; or other clinical evidence of hypoxemia (e.g., cyanosis). Based on the recent report from Rice TW et al., additional criteria to determine hypoxemia representative of ARDS will be included as follows: ratio of SpO2/FiO2 <315; where FiO2 will be calculated for patients receiving oxygen by cannula or mask as follows: 1 liter = 0.21; 2 liters = 0.23; 3 liters = 0.25; 4 liters = 0.3; 5 liters = 0.35; 6 and 7 liters = 0.45, and 8,9, and 10 liters = 0.49 (Rice TW 2007).
- 2. Bilateral infiltrates on frontal chest radiograph (obtained within 24 hours of Completion of transfusion) must be present. There must be absence of left atrial hypertension (i.e., circulatory overload). However, if ALI is diagnosed by the expert panel in the presence of left atrial hypertension, the case may be classified as TRALI/TACO (overlap case).

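### Section L counts TACO only from panel-classified cases, but F5 ends review at triage once moderate-to-severe TACO is recorded, so the planned TACO incidence omits its clearest cases

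*Protocol*

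**What the plan says.** **TACO numerator.** Section L, among the additional analyses, states that "incidence for transfusion-associated cardiac overload will be based on cases that are classified by the Medical panel as TACO". The same section plans to explore associations between the complications, TACO among them, and clinical characteristics.

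**Triage step.** F5 puts one physician between the hypoxemia screen and the panel: "The review will be performed by a single MD". On the task itself: "The major aspect of this review is to determine if there is sufficient information to conclude that the patient has moderate to severe TACO". If so, "the triage MD will complete the form indicating the presence of TACO and no further reviews will be required". On volume: "The number of cases that will be excluded from further review by the triage MD is uncertain, but may amount to 50" per cent of the charts. Section P of the extended form (Appendix G) records the triage TACO diagnosis, to be ticked only on clear evidence. It has a separate yes/no item on whether expert review is needed, and no item on ALI.

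**Table-4.** The comment on the same step reads: "An unknown number of cases will be diagnosed as TACO and will have no evidence for ALI". It says that these cases need not go to the board.

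**Panel.** F21 sets up a board of three physicians, distinct from the triage physician. Both TACO and TRALI/TACO overlap are among its diagnoses. F25 item 2 ties the overlap label to the panel diagnosing ALI when left atrial hypertension is present.

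**Late ALI.** Section L also plans, when possible and among recipients with other risk factors, an incidence for "ALI that is not TRALI but that occurred within 6 hours or >6 hours of transfusion". F4 and Section E of the extended form end review unless hypoxemia is found within six hours of completing the transfusion.

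**The concern.** Section L fixes a numerator that the workflow cannot fill. A case closed at triage has a TACO diagnosis on the form but no panel classification, so under the literal rule it is not counted. The cases removed are those with clear evidence of moderate-to-severe disease. Those left are the ones triage could not settle. The published TACO incidence would be too low, and any association analysis built on the same definition would describe a selected remainder.

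Two related wordings compound this:

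- F5 stops review on TACO alone, while Table-4 describes the stopped cases as TACO without evidence of ALI. These are different rules for a recipient who may have both, and only the panel can assign the overlap category.
- The incidence of ALI beyond six hours is to be drawn from charts that had to show hypoxemia within six hours to be kept.

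**Working it through.** **Step 1: reproduce the number of charts at triage.** Inputs from F3 to F5 and Table-4: 2,590 recipients, 40% with a post-transfusion chest x-ray, 50% of those with new or worsening bilateral infiltrates, 60% of those hypoxemic.

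- 2,590 × 0.40 = 1,036
- 1,036 × 0.50 = 518
- 518 × 0.60 = 310.8, i.e. 311

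All three agree with the protocol.

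**Step 2: charts outside the Section L numerator.** Let *f* be the share removed at triage. All removals are taken to be TACO, the only ground for stopping that F5 gives. Missing cases = 311 × *f*, and missing incidence = 311 × *f* / 2,590. Only 50% comes from the protocol. The other values are assumptions that show the range.

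| *f* | Missing charts | Share of 2,590 |
|---|---|---|
| 10% | 31 | 1.2% |
| 25% | 78 | 3.0% |
| 50% (F5) | 155 (155.5) | 6.0% |
| 75% | 233 | 9.0% |

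**Step 3: how much identified TACO the panel-only rule would capture.** Let *s* be the share of forwarded charts that the panel calls TACO. The protocol gives no value, so 5% to 40% is assumed. Panel TACO = 311 × (1 − *f*) × *s*. Captured share = panel TACO / (311 × *f* + panel TACO).

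| *f* | *s* | Panel only | Triage + panel | Captured |
|---|---|---|---|---|
| 50% | 5% | 7.8 (0.3%) | 163.3 (6.3%) | 5% |
| 50% | 40% | 62.2 (2.4%) | 217.7 (8.4%) | 29% |
| 25% | 5% | 11.7 (0.45%) | 89.4 (3.45%) | 13% |
| 25% | 40% | 93.3 (3.6%) | 171.1 (6.6%) | 55% |

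**Step 4: does this reach the primary analysis?** No. Fisher's exact test at 2.32% versus 0.79%, with 1,175 per group and one-sided 0.05, has exact power of 90.0%. This matches Appendix D, and nothing in that calculation uses the TACO count.

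**Step 5: overlap cases.** F5 gives a stop with no ALI condition. Table-4 gives a stop with one. Section P has no ALI item on which compliance could be checked, but it allows the reader to tick TACO and still ask for expert review. The protocol gives no overlap rate, so no number of affected cases can be derived.

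**Step 6: late ALI.** Any one of four oxygenation items within six hours passes the Section E screen, whatever the cause and whether or not the hypoxemia is new. Late ALI with some early hypoxemia can therefore be seen. Late ALI without it cannot.

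**The case against.** The best defence is that little depends on this. TACO incidence is neither a primary nor a secondary objective (C1, C2). The triage diagnosis is recorded for each case, so no data are lost and an analyst could add it back. F5 calls the removal share uncertain and Table-4 calls it unknown, so 155 is not a forecast. All of this stands, and it limits the weight of the point. It does not remove the conflict: Section L names the source of the numerator, and that source excludes the triage cases.

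Two stronger readings are tempting.

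- **Overlap.** A reader might infer that TRALI/TACO overlap cases are cut off by a single physician, with a loss that matters against the roughly 40 TRALI cases expected. The documents do not support this. Section P contains no instruction to stop and has its own referral item, and Table-4 already restricts non-forwarding to cases without evidence of ALI. Under that wording no overlap case is stopped. The protocol also does not say that overlap cases count as TRALI. What remains is a risk under F5's wording.
- **Late ALI.** A reader might infer that the late-ALI incidence will be near zero by construction, because Note 21 of Appendix G dates a reaction to the first abnormal ratio or x-ray. That note is attached to the vital-signs table, and nothing binds the panel to date ALI by it. Early hypoxemia of any cause passes the screen, x-rays are accepted to 24 hours, blood gases are recorded to 35 hours 59 minutes, and Section L says that these incidences are calculated when possible. Under-ascertainment is shown; a value near zero is not.

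**Conclusion.** The conflict between Section L and F5 holds. Followed as written, the TACO incidence omits every case settled at triage: about 155 recipients (6.0% of 2,590) at F5's possible 50% removal, and 31 to 233 (1.2% to 9.0%) for an assumed 10% to 75%. These figures rest on the protocol's own planning rates and on triage removals being TACO. The share captured by the panel-only rule (5% to 29% at 50% removal) also depends on an assumed panel TACO rate.

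F5 and Table-4 disagree on whether absence of ALI is needed to stop review. That must be reconciled, but loss of overlap cases is not established and cannot be sized. The incidence of ALI beyond six hours is under-ascertained for recipients without early hypoxemia, by an amount the documents do not allow one to compute.

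The TACO numerator does not affect the primary TRALI comparison or its sample size. The correction should be made because it is easy and the reported TACO figure would otherwise mislead.

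**What to change.** 1. **Section L, TACO.** Define TACO as cases recorded by the triage physician on Section P plus cases classified as TACO by the panel. Report the two components separately as well as together, and use the combined definition in the association analyses.
2. **F5 and Table-4.** Make the two stopping texts agree on the role of ALI. The simplest way is to carry Table-4's condition into F5, add an item on evidence of ALI to Section P, and say that a chart with both goes to the panel.
3. **Section L, late ALI.** State that the incidence beyond six hours covers only recipients who also met the six-hour hypoxemia screen, and that it is therefore under-ascertained.

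The first and third changes are wording only, because the triage diagnosis is already collected. The second costs a sentence, one form item and possibly some additional panel reviews. None changes the primary test or the sample size.
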